#### **4.4.3. Handling of Outliers**

There will be no exclusion of outliers, all measured values will be included in the analyses.

#### **4.4.4. Stratification Factors**

Not applicable.

### **4.5. Presentation of Results**

#### **4.5.1. Presentation of Treatment Groups**

Results will be presented by treatment group:

- GLPG3970 400 mg qd
- Placebo

In the Subject Information, a grand total “All Subjects” will be added to summarize all subjects over all treatment groups in tables.

#### **4.5.2. Calculation of Descriptive Statistics**

For continuous parameters, descriptive statistics will be presented when  $N \geq 2$ . When  $N = 1$ , the observation will not be shown in tables nor in figures of summary statistics but will only be listed.

Descriptive statistics will include:

- the number of non-missing data points (n);
- the arithmetic mean;
- the standard error (SE) and standard deviation (SD);
- the median, minimum and maximum;
- 90% confidence interval (CI) of the mean (if indicated in the relevant section).
- Some parameters namely estimated glomerular filtration rate (eGFR), C-reactive protein (CRP), [REDACTED] and metabolic parameters (fasted insulin, homeostatic model assessment of insulin resistance (HOMA-IR) and HbA1c) are known to deviate heavily from the normal distribution but follow the log-normal distribution well. For these parameters, the geometric mean (GM), geometric standard deviation (GSD), and geometric standard error (GSE) will be also reported for the summaries by treatment group and visit. GM, GSD and GSE are not applicable for the summaries of the changes from baseline, however GM, GSD and GSE will be reported for the summaries of percent changes from baseline. This will be done by obtaining the mean, SD and SE of  $\log(\text{value}) - \log(\text{baseline})$  and then transforming these statistics back to the 'percent change scale' as  $100 \times \{\text{exponential}(\text{statistic}) - 1\}$ .

For PK data, descriptive statistics will include:

- the number of non-missing observations (n);
- the number of data points above the LLOQ;
- the arithmetic mean;
- SE and SD;
- the median, minimum and maximum;
- the CV%;
- the geometric mean and geometric CV%.

If less than 50% of the subjects have quantifiable values, only the number of subjects with data, number of data points above the LLOQ, the arithmetic mean, median, minimum, and maximum will be presented with the original calculated value. The other descriptive statistics will be listed as “NC” (not calculated).

If the calculated descriptive statistic is BLOQ, then it will be presented as “BLOQ”.

Individual values and descriptive statistics of concentrations and PK parameters will be presented with 3 significant digits.

#### **4.5.3. Calculation of Percentages**

Frequencies and percentages will be generated for categorical parameters.

For event-type data (e.g. adverse events), the denominator will be all subjects in the analysis set and analysis period. For other data (e.g. worst-case analysis of assessments), the denominator will be all subjects with (post-baseline) data for the parameter, in the analysis set and analysis window/period.

### **5. INTERIM ANALYSES AND INTERNAL DATA SAFETY MONITORING COMMITTEE**

No formal interim analysis is planned for this clinical study.

A Safety Monitoring Committee independent from the study will review unblinded data during the course of the study. This Committee will include a physician with experience in drug development, a biostatistician, and a safety physician. External medical experts (such as an expert in the field of pSS and an infectious diseases expert) may be included to support data interpretation. The Committee will review unblinded safety data and assess any potential safety issues arising during the conduct of the clinical study, including (but not limited to) any potential issues in the context of the SARS-CoV-2 pandemic. The process is described in a separate ‘Safety Monitoring Committee Charter’.

## 6. STATISTICAL ANALYSES

### 6.1. Subject Information

Subject information will be tabulated using the Safety Analysis Set, unless specified otherwise. No inferential testing will be performed, nor will p-values be provided.

Subject information will be tabulated with descriptive statistics per planned treatment group, as well as overall.

[figure not shown]
#### 6.1.1. Demographic and Baseline Disease Characteristics

The following parameters will be summarized:

- date of ICF signature (listed);
- sex;
- age at signing the ICF (years);
- age, categorized (years):  $18 \leq \text{age} < 65$ ;  $65 \leq \text{age} \leq 74$ ;
- race and ethnicity;
- height at baseline (cm);
- weight at baseline (kg);
- body mass index (BMI) at baseline ( $\text{kg}/\text{m}^2$ ) = 
$$\frac{\text{weight} \ (\text{kg})}{\text{height}^2 \ (\text{m}^2)} ;$$
  
(BMI will not be recalculated if already available in the database)
- duration of Sjogren's Syndrome disease (years)  
$$= \frac{(\text{date of first study drug administration}) - (\text{date of diagnosis}) + 1 \text{ day}}{365.25}$$

For the date of diagnosis, if missing month, impute as January (01), if missing day, impute as the first day of the month (01).

- duration of Sjogren's Syndrome disease, categorized (years):  $< 1$ ;  $1 \leq \text{duration} < 5$ ;  $5 \leq \text{duration} < 10$ ;
- ESSDAI at baseline;
- ESSPRI at baseline;

Demographic and baseline disease characteristics will be listed.

### **6.1.2. Allocation and Randomization**

The number of subjects (and percent) per treatment group and overall will be tabulated per country and site.

The following listings will be provided:

- Listing per subject of the IP kit numbers, IP lot numbers dispensed/returned.
- Randomization schemes and codes, with the treatment assigned to each subject. This listing includes a flag in case of discrepancies or errors between the assigned and the actual treatment taken, and should also include flags declaring any (potential) unblinding.

### **6.1.3. Disposition Information**

The following tabulations will be provided, by treatment group and overall:

- The number of subjects screened, not-randomized (including reasons), randomized (treated and not treated), and treated with GLPG3970 and Placebo.
- Number (percent) of subjects randomized per country and site.
- The number (percent) of subjects in each analysis set as defined in [Section 4.1](#).
- The number (percent) of subjects per analysis window as defined in [Section 4.3.3](#).
- The number (percent) of subjects who completed/discontinued the IP administration schedule and the reasons for discontinuation.
- The number (percent) of subjects who completed/discontinued the study and the reasons for discontinuation.

Subjects who discontinued early from study or treatment will be listed. Discontinuation related to SARS-CoV-2 will be flagged in the listing.

Additionally, the following information will be provided in listings:

- Subject identification and randomization (country, site number, investigator, subject number).
- Randomization number and date planned and actual randomization group, with flags for any discrepancies.
- Subjects excluded from the safety and full analysis sets.
- First and Last Key Dates in the Study will be listed.

#### **6.1.4. Protocol Deviations and Eligibility**

Major protocol deviations are determined and recorded while the study is ongoing, and the list is finalized prior to database lock (and unblinding). For more details, please refer to the Protocol Deviations Plan.

The number (percent) of subjects with major protocol deviations will be tabulated, overall and per class of deviation, by treatment group and overall.

All available information concerning major protocol deviations, including COVID-19 related verbatim, violations on eligibility criteria and subjects not treated will be listed. Protocol deviations leading to the exclusion of subjects from any analysis set, as applicable, will be flagged.

Minor protocol deviations will not be tabulated and will be listed.

#### **6.1.5. Medical History and Concomitant Diseases**

Frequency tabulations, per treatment group and overall, per system organ class and preferred term will be provided for the medical history findings (i.e., conditions no longer present at the start of the study) as well as for the concomitant diseases (i.e. conditions present at the start of the study) using Medical Dictionary for Regulatory Activities (MedDRA) coding dictionary.

All medical history findings and concurrent diseases will be listed separately.

#### **6.1.6. Prior and Concomitant Medications**

##### **6.1.6.1. Coding of Reported Terms**

All prior and concomitant therapy terms will be coded in the database using the World Health Organization (WHO) drug coding dictionary.

##### **6.1.6.2. Classification of Therapies**

All prior and concomitant medication records will be categorized as follows, considering their date and flags indicating the relative timing versus study (drug) start or end (before, after, ongoing):

- Prior only: when the record ended before the first IP administration date.
- Concomitant only: when the record started on or after the first IP administration date.
- Prior and concomitant: when the record started before the date of first IP administration, and ended on or after this point, or continued.

When the start or end date of the prior and concomitant medication records are incomplete (and no flags indicating relative timing are available), the date of first IP administration will be considered to the same level of information provided by these incomplete dates to categorize the timing of these records. This means that a record only having month and year will be categorized

comparing only to the month and the year of the date of first IP administration. The record only having year will be categorized comparing only to the year of the date of first IP administration.

#### 6.1.6.3. Calculation of Relative Days

If both the start and the end dates of the concomitant medication records are completed, their day relative to the day of first IP administration will be calculated as described in [Section 4.3.1](#).

#### 6.1.6.4. Presentation of Results

A frequency tabulation per planned treatment group and overall of the Anatomical Therapeutic Chemical (ATC) classification classes level 4 by therapeutic subgroup (ATC level 2) and generic term of the prior medication (defined as 'prior only' and 'prior and concomitant') will be provided as well as of the concomitant medication (defined as 'concomitant only' and 'prior and concomitant').

A listing of prior and concomitant medications will be provided. Also, prior and concomitant corticosteroid listing will be provided separately (the list of the ATC codes to be selected in this listing will be provided by the Galapagos medical services).

#### 6.1.7. Procedures

Procedures results will only be listed.

#### 6.1.8. Exposure to Study Drug and Compliance

##### 6.1.8.1. Derivation Rules

###### Derived Parameters: Extent of Exposure to IP

- *Total treatment duration* (days) = last IP administration date – first IP administration date + 1 day, inclusive, regardless of temporary interruptions in IP administration.
- *Total treatment duration, excluding days off IP*: Sum of the number of days with any IP administration.
- *Total treatment duration, full compliance* (days): Number of days where IP has been taken.

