7.2. Dosage and Administration

GLPG3970 will be provided as a film-coated tablet containing 200 mg of the active pharmaceutical ingredient G1567970 (G1567970 is the compound code for GLPG3970). A dose of 400 mg (2 x 200 mg tablets) q.d. will be taken orally.

At all dosing days, the IP needs to be taken q.d. at approximately the same time every morning in a fed state (together with a meal), except at Visit 1 (Day 1) when the IP will be taken in a fasted state. At Visit 1 (Day 1), breakfast will be provided to the subject 0.5-1 hour after the IP intake and lunch should be eaten 1 hour before or after the ECG measurement at 4.5 hours postdose. Subjects will be instructed to swallow the tablets of GLPG3970 or placebo as a whole with a glass of water and to not chew the drug prior to swallowing. At Visit 1 (Day 1), IP will be administered on site after predose assessments have been completed. At Visit 2, 3, 4, and 5, subjects also need to take their IP on site.

Subjects will receive tablets to take home. Instructions for dosing and storage are incorporated in the IP labels.

If a subject misses a dose (e.g. because he/she forgot to take the medication), he/she should take the missed dose within 12 hours after the planned intake time. If IP is not taken within 12 hours

after the planned time, the missed dose should be skipped. For each dose taken at home, the time, date, and number of tablets taken should be recorded in the subject's diary card.

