### 2.2.3. Other Endpoints

## 2.3. Study Design

This is a Phase 2a, randomized, double-blind, placebo-controlled, parallel-group, multicenter study to evaluate the efficacy, safety, tolerability, PK, [REDACTED] of orally administered GLPG3970 for 12 weeks in adult subjects with active pSS.

One dose level of GLPG3970 will be evaluated in 30 subjects who will be randomized 2:1 to receive GLPG3970 (400 mg [2 x 200 mg] qd) or matching placebo, respectively.

The study will consist of 3 study periods:

[figure not shown]
- Screening period: up to 4 weeks with 1 study visit. During the Screening visit, subjects will be selected based on the eligibility criteria. Subjects already on treatment will remain on a stable standard of care (SoC) treatment during the study.
- Treatment period: 12 weeks with up to 5 study visits (Days 1, 8, 29, 57, and 85). At any time during the course of the study, phone calls or unscheduled visits can be added if deemed necessary by the investigator. Subjects will receive GLPG3970 or placebo qd.
- Follow-up (FU) period: 4 weeks with 1 study visit. Subjects remain on stable SoC treatment, if applicable.

The subjects will be in the study for a duration of 20 weeks: up to 4 weeks of screening, 12 weeks of treatment, and 4 weeks of FU.

Refer to the Schedule of Assessments ([Section 2.5](#)) for further details.

A schematic diagram of clinical study design and periods is provided in [Figure 1](#).

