### 6.1.8.2. Presentation of Results

Summary statistics per planned treatment group and overall will be provided for each compliance and extent of exposure parameter for IP administration. Frequency tables will be provided for the compliance parameters, using the following categories: <80%; 80%  $\leq$  x < 100%; 100%; 100%  $\leq$  x < 120%; > 120%.

All original IP administration records will be listed per subject. The listing will include all deviations from IP schedules such as missed or reduced doses and GLPG3970/placebo switches. IP exposure and compliance data will be listed.

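### SAP 6.1.8.1: full-compliance days are the same count as any-intake days, so the full-compliance percentage cannot register a partly taken daily dose

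*SAP*

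**What the plan says.** **Dose and records.** Protocol 7.2 sets the regimen: "A dose of 400 mg (2 x 200 mg tablets) q.d. will be taken orally". For home doses, the "time, date, and number of tablets taken should be recorded" in the diary card. Protocol 7.5 has the CRF record IP administration by amount as well as by period.

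**Durations.** SAP 6.1.8.1 derives three:
- Total treatment duration: "last IP administration date – first IP administration date + 1 day, inclusive, regardless of temporary interruptions in IP administration".
- Duration excluding days off IP: "Sum of the number of days with any IP administration".
- Duration with full compliance: "Number of days where IP has been taken".

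**Percentages.** The same section then derives three compliance percentages. Overall compliance is doses actually taken over doses due. The other two divide the second and third durations above by total treatment duration.

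**Presentation.** SAP 6.1.8.2 states: "Frequency tables will be provided for the compliance parameters". The classes run: below 80%, 80% to below 100%, 100%, 100% to below 120%, and above 120%. The same section lists all IP administration records by subject, with missed and reduced doses included.

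**The concern.** A plan that names any-intake days and full-compliance days separately, and reports a percentage for each, evidently wants two different pieces of information: whether the subject took anything that day, and whether the subject took the whole dose. As worded, both definitions answer only the first question. With a two-tablet dose the difference matters, because a one-tablet day is possible, can be identified from the collected data, and is foreseen by the SAP's own listing of reduced doses.

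What is at stake is the accuracy of a labelled summary. A table row headed full compliance would be read as the share of days on the complete planned dose, and the stated rule does not deliver that. The class boundaries add a smaller difficulty: a subject at exactly 100%, the value for anyone with no missed day, belongs to two classes, and one at exactly 120% belongs to none.

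**Working it through.** The documents state no compliance figure to reproduce, so the check applies the SAP rules to daily tablet counts.

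**Inputs**
- Planned tablets per day: 2 (Protocol 7.2).
- Treatment period: 12 weeks (SAP 2.3), so 84 days, or 85 if a dose is also taken at the Day 85 visit.
- Formulas: SAP 6.1.8.1.

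**Notation.** Let D be total treatment duration and t the number of tablets taken on a day.
- Any-intake days, A = number of days with t > 0.
- Full-compliance days as written, F = number of days on which IP was taken = number of days with t > 0.
- Complete-dose days, C = number of days with t = 2 (comparison rule, no instructed reduction assumed).

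A and F are the same count, so 100 × A/D = 100 × F/D for every subject. As a numerical check, 10,000 random 84-day records with 0, 1 or 2 tablets per day, and dosing on the first and last day, gave identical percentages in every record.

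**Worked cases, D = 84 (168 tablets due)**

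| Pattern | Any intake | Full compliance as written | Complete-dose days | Overall, dose = tablet | Overall, dose = daily intake |
|---|---|---|---|---|---|
| 2 tablets every day | 84/84 = 100% | 84/84 = 100% | 84/84 = 100% | 168/168 = 100% | 84/84 = 100% |
| 1 tablet every day | 84/84 = 100% | 84/84 = 100% | 0/84 = 0% | 84/168 = 50% | 84/84 = 100% |
| 1 tablet on 42 days, 2 on 42 days | 84/84 = 100% | 84/84 = 100% | 42/84 = 50% | 126/168 = 75% | 84/84 = 100% |
| 2 tablets, 13 whole days missed | 71/84 = 84.5% | 71/84 = 84.5% | 71/84 = 84.5% | 142/168 = 84.5% | 71/84 = 84.5% |

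With D = 85 the first two rows are unchanged. The third becomes 43/85 = 50.6% for complete-dose days and 128/170 = 75.3% for overall compliance in tablets.

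**Reading the table.** Wholly missed days are handled correctly. Only partly taken days go unregistered. The overstatement is 100 × (F − C)/D, which is the share of treatment days with an incomplete dose. Whether overall compliance picks up those days depends on what a dose is, and SAP 6.1.8.1 does not define it.

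**Categories.** The two percent-days measures cannot exceed 100%, because their numerators count days within D. The classes above 100% therefore concern overall compliance only. The double placement of exactly 100% affects all three measures.

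**The case against.** **Under-dosing is not hidden.** This is the strongest objection, and it stands. A reader might infer from the equal definitions that partial dosing would never show in the results. The documents do not support that. SAP 6.1.8.2 lists every administration record, reduced doses included, and overall compliance gives 50% for the one-tablet subject if doses are counted as tablets. What remains is that two of the three summary percentages cannot show it, and the third may not.

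**No estimate depends on the metric.** This also stands. Lack of compliance is handled by treatment policy in SAP 3. The analysis sets (SAP 4.1), the MMRM (SAP 6.2.2.2) and the hepatotoxicity tables (SAP 6.3.2.8) make no use of it. A reader might infer that the efficacy or liver-safety results are distorted; nothing in the plan links them to this percentage.

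**It may be settled elsewhere, or moot.** SAP 1 puts technical derivation details in a separate document, which is not available here, and the label suggests loose wording rather than intent. SAP 1 also marks provisions dropped after early termination in grey, which the text at hand does not show, so it cannot be confirmed that the table is still produced. Both are fair cautions, but neither makes the wording under Derivation Rules correct.

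**One-tablet days may be rare.** The documents give no expected frequency, so the worked cases show how the rule behaves and do not forecast results.

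**The class boundaries may be a reading artefact.** The inequality signs come from a PDF read by a program, so the published table should be checked.

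**Conclusion.** The point holds as a minor error in a derivation rule. As written, *Percent days full compliance* duplicates *Percent days with any intake* and is overstated by the share of days with an incomplete dose. The worst case is 100 percentage points: 84/84 = 100% as written against 0/84 = 0% on complete-dose days. Setting the 100% against the 50% of the dose actually taken would compare a share of days with a share of tablets; the like-for-like contrast is 100% against 0%.

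The consequence is confined to the exposure and compliance summaries. The conclusion assumes that the separate derivation document does not override the SAP wording, that the table is still produced after early termination, and, for the worked cases, that two tablets are planned every day.

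The last assumption needs care. Protocol 6.4 and Appendix 15 mention reduction of IP for some transaminase elevations, while the action-taken options in Protocol 11.2.1 include no reduced dose. A threshold fixed at two tablets could score a subject who followed an instructed reduction as non-compliant, so the rule should refer to the number planned for the day.

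**What to change.** - **SAP 6.1.8.1, full compliance:** count a day as fully compliant when the number of tablets taken, active or placebo, equals the number planned for that day, using the diary and CRF. Keep any-intake days as they are.
- **SAP 6.1.8.1, overall compliance:** state that doses are counted as tablets, in both numerator and denominator.
- **SAP 6.1.8.2, categories:** use <80%, 80% to <100%, 100%, >100% to 120%, and >120%.
- **Instructed reductions:** reconcile Protocol 6.4, Appendix 15 and 11.2.1, and state in the SAP how days of any instructed reduction count against the planned dose. This is a counting convention and implies no view on the clinical rule.

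The cost is a few lines of SAP text and the matching programming specification. Tablet counts and administered amounts are already collected under Protocol 7.2 and 7.5, so no new data are needed, and no analysis set, model or sample size changes.

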###### Derived Parameters: Compliance

- Overall compliance (%) =  $100 \times \frac{\text{number of doses actually taken}}{\text{number of doses that should have been taken}}$
- Percent days with any intake (%) =  $100 \times \frac{\text{total treatment duration, excluding days off drug}}{\text{total treatment duration}}$
- Percent days full compliance (%) =  $100 \times \frac{\text{total treatment duration,fully compliant}}{\text{total treatment duration}}$

### 6.1.8.2. Presentation of Results

Summary statistics per planned treatment group and overall will be provided for each compliance and extent of exposure parameter for IP administration. Frequency tables will be provided for the compliance parameters, using the following categories: <80%; 80%  $\leq$  x < 100%; 100%; 100%  $\leq$  x < 120%; > 120%.

All original IP administration records will be listed per subject. The listing will include all deviations from IP schedules such as missed or reduced doses and GLPG3970/placebo switches. IP exposure and compliance data will be listed.

